11.2. Appendix 2: Time & Events

11.2.1. Protocol Defined Time & Events

Study Procedures	Visit 1a Pre-Screen	Visit 1b** Screening (V1a + 14 days)	Visit 2 Baseline (V1b + 28d ± 4 days)	Visit 3 (Baseline + 13 wks ± 14 days)	Visit 4 (Baseline + 26 wks ± 14 days)	Visit 5 (Baseline + 39 wks ± 14 days)	Visit 6 (Baseline + 52 wks ± 14 days)	Visits 7 - 9 (Years 2, repeat as for V3-V5 of Year 1)	Visit 10 (Baseline + 104 wks ± 14 days)
	Pre-Screen Visit	Start of Placebo run-in	Start of Treatment Phase Baseline (Randomization)	3 months post Randomization (Rand)	6 months post Rand	9 months post Rand	12 months post Rand	15,18 & 21 months post Rand respectively	End of Treatment Phase 24 months post Rand ⁱ
ICF	X								
Inclusion/Exclusion	X	X							
Medical Hx/ Demog/CV Hx/	X								
ECG (12-lead)		X							
Collection of PGx Sample			X						
Safety evaluations									
Concomitant medication	X	X	X	X	X	X	X	⇒	X
Physical Examination ^a		X			X		X	X ^h	X
Vital signs ^b		X	X	X	X	X	X	⇒	X
Haematology/clinical chemistry	X						X		X
HBsAg and Hepatitis C Antibody ^g			X						
Total serum PSA ^c	X				X		X		X
Post-void residual volume (PVR)	X	X***	X		X		X	X ^h	X
AEs ^d		X	X	X	X	X	X	⇒	X
Suicidality (C-SSRS)	X				X		X		X
Efficacy:									
BPH symptoms (IPSS)	X		X	X	X	X	X	⇒	X
Prostate Volume (TRUS)		X					X		X

Study Procedures	Visit 1a Pre-Screen	Visit 1b** Screening (V1a + 14 days)	Visit 2 Baseline (V1b + 28d ± 4 days)	Visit 3 (Baseline + 13 wks ± 14 days)	Visit 4 (Baseline + 26 wks ± 14 days)	Visit 5 (Baseline + 39 wks ± 14 days)	Visit 6 (Baseline + 52 wks ± 14 days)	Visits 7 - 9 (Years 2, repeat as for V3-V5 of Year 1)	Visit 10 (Baseline + 104 wks ± 14 days)
	Pre-Screen Visit	Start of Placebo run-in	Start of Treatment Phase Baseline (Randomization)	3 months post Randomization (Rand)	6 months post Rand	9 months post Rand	12 months post Rand	15,18 & 21 months post Rand respectively	End of Treatment Phase 24 months post Rand ⁱ
Peak Urine Flow (Qmax)	X	X ^{**}	X		X		X	X ^b	X
AUR or BPH-related Surgery			X	X	X	X	⇒	X	X
Pharmacokinetics^j									
Serum PK samples ^j				X	X	X			
Health Outcomes:									
BPH Health Status Q 8 IPSS (BHS)	X		X	X	X	X	X	⇒	X
AUR or BPH-related Surgery Medical Resource Utilisation			X	X	X	X	X	⇒	X
BPH Impact Index (BII)	X		X	X	X	X	X	⇒	X
PAS-SFI		X	X				X		X
Other Efficacy Measures									
UTI /Incontinence / Renal Insufficiency			X	X	X	X	X	⇒	X
Register in RAMOS	X								
Study Medication:									
Call RAMOS/DispenseMeds		X ^e	X ^f	X	X	X	X	⇒	
Compliance check/Collection			X	X	X	X	X	⇒	X

Protocol Defined Time & Events, Notes

** This second screening visit is mandatory before dispensing placebo run-in medication. This additional screen visit is designed to allow time for PSA/haem/biochem results to be returned from the laboratory, and repeat Qmax/PVR (if required) before performing TRUS on patients who may not otherwise be eligible for the study.

***REPEAT ONLY IF QMAX inclusion criteria NOT MET at Visit 1a

⇒ ongoing assessment

- a. Including DRE and qualitative breast examination
- b. Blood pressure and pulse to be taken after sitting quietly for 5 minutes

- c. PSA sample must be taken before TRUS
- d. Only Serious AEs (related to study participation) occurring between Screening (Visit 1a) and the start of placebo run-in medication need to be recorded
- e. Single-blind medication to be dispensed at Visit 1b only
- f. Double-blind medication dispensed from Visit 2 onwards.
- g. Hepatitis B surface antigen and hepatitis C antibody (if hepatitis C antibody positive, a hepatitis C RNA test should be reflexively performed to confirm the result)
- h. Only performed at Visit 8 (Month 18)
- i. Performed for End of Study Treatment Assessments as well when a subject discontinues the study treatment.
- j. Serum PK samples are only applicable to subjects of Chinese origin living in China.

11.3. Appendix 3: Assessment Windows

Boundaries for the scheduled assessments are defined in the protocol. The data will be summarized by nominal visit without regard to window days for all scheduled visits. The efficacy, safety, and health outcomes measures collected at nominal visits include IPSS, prostate volume, Qmax, PSA, post void residual volume, BII, BPH-related Health Status, and PAS-SFI. In order to utilize as much data as possible in these efficacy, safety, and health outcomes summaries and analyses, premature withdrawal visit data will be used as the scheduled visit data when both of the following criteria are met:

- The scheduled visit evaluation is not available, and
- The premature withdrawal visit date falls within 30 days (inclusive) for each of the scheduled post baseline visits (i.e., Months 3, 6, 9, 12, 15, 18, 21, and 24), or within 15 days (inclusive) of the scheduled Baseline visit (Month 0). The scheduled visit day for month k will be calculated as:
Baseline Date + (k * 365/12) rounded to the nearest integer.

11.4. Appendix 4: Multicenter Studies

11.4.1. Methods for Handling Centers

The 4 countries which randomized subjects into this trial include: China, Japan, Korea, and Taiwan. Forty-six centers across these 4 countries randomized subjects into this trial.

Clusters will be used in the exploration of center effect and treatment-by-center interaction.

As stated in the protocol, it was anticipated that randomized subject accrual would be spread thinly across centers and summaries of data by center would be unlikely to be informative. It was expected that investigative centers would be pooled a priori into clusters based on geographic location. As stated in protocol, these clusters would be identified once randomization was complete and then used in statistical analyses in the exploration of center effects and treatment-by-center interaction.

Based on the actual randomization of sites within countries, it is reasonable and logical to assign each country as a single cluster. Therefore, the 4 clusters are the 4 countries: China, Japan, Korea, and Taiwan. The countries will be used in summaries of randomized subjects, subgroup summaries, and in statistical analyses of efficacy center effect and treatment-by-center interaction; these by-country summaries and analyses are described in relevant sections.

11.5. Appendix 5: Data Display Standards & Handling Conventions

11.5.1. Study Treatment & Sub-group Display Descriptors

Treatment Group Descriptions			
RandAll NG [1]		Data Displays for Reporting	
Code	Description	Description	Order [2]
A	Dutasteride 0.5mg once daily + tamsulosin 0.2mg once daily	Dut 0.5mg + Tam 0.2mg	2
B	Dutasteride placebo once daily + tamsulosin 0.2mg once daily	Placebo + Tam 0.2mg	1

NOTES:

1. RandAll NG (Next Generation) is a randomization creation and publishing tool for GSK studies.
2. Order represents treatments being presented in tables, listings, and figures.

Within this RAP, the following additional references may be made for brevity:

--Full Treatment Description--	--Short Treatment Descriptions--
Dutasteride 0.5mg once daily + tamsulosin 0.2mg once daily or	-Combination -Dut 0.5mg + Tam 0.2mg -Dut + Tam
Dutasteride placebo once daily + tamsulosin 0.2mg once daily	-Tamsulosin Monotherapy -Tam 0.2mg -Placebo + Tam 0.2mg -Tam

11.5.2. Reporting Process & Standards

The following reporting process and reporting standards details apply to all RAP defined endpoints.

Reporting Process	
Software	

 SAS software will be used for all analyses except when noted. It is anticipated that the SAS software version 9.3 will be in use at statistical analysis complete; use of a version other than 9.3 will be documented in IMMS Study File. 	
Reporting Areas The following server and areas are identified as of RAP finalization. Revisions to these areas, for example due to platform / server relocation and/or CDISC reporting standards, will be documented in IMMS Study File.	
HARP Server	US1SALX00259
HARP Area	The high level area is defined as: /arenv/arprod/gi198745/ari114265/final.
QC Documentation Area	QC process and documentation for analysis and reporting will be maintained as a text file on HARP server US1SALX00259 within above noted area.
Analysis Datasets	

 Analysis datasets for international regulatory submissions will not be created according to CDISC standards. GSK exemption for ARI114265 CDISC-based dataset creation and reporting was granted in June 2016. 	
Generation of RTF Files	

 RTF files will be generated for all tabular summaries with the reporting efforts described in the RAP unless clearly stated as not required by the assigned Scientific and Medical Writer(s). 	

Reporting Standards	
General	

The current GSK Integrated Data Standards Library (IDSL) and GSK IDSL Statistical Principles will be applied for reporting, unless otherwise stated within RAP text or indicated in table, listing, figure shells:
 
 4.03 to 4.24: General Principles 5.01 to 5.08: Principles Related to Data Listings 6.01 to 6.11: Principles Related to Summary Tables 7.01 to 7.13: Principles Related to Graphics 	

From the above standards and principles as well as to be aligned with historical reporting for this compound and indication, the key reporting standards to be applied are:
 
 All data will be reported according to the actual treatment the subject received unless otherwise stated. Within listings, numeric data will be reported at the precision collected on the eCRF. The reported precision from non eCRF sources will follow the IDSL statistical principles but may be adjusted to a clinically interpretable number of decimal places. Within tabular summaries, the minimum and maximum values are presented with the same 	

Reporting Standards

number of decimal places as the raw data collected on the eCRF. The mean and percentiles (e.g. median, Q1, and Q3) are presented using one additional decimal place. The standard deviation and standard error are presented using two additional decimal places.

- Continuous variables (e.g., age) will be summarized using the number of observations (n), mean, standard deviation (SD), median, minimum, and maximum.
- Categorical variables will be summarized using the number of subjects (n) and percentage (%) in each category.
- P-values greater than 0.10 will be reported to two decimal accuracy. P-values less than or equal to 0.10 will be reported to three decimal accuracy. P-values less than 0.001 will be reported as '<0.001'.
- Applicable safety analysis and reporting definitions and presentations within "Program Safety Analysis Plan ([PSAP](#)) for GI198745 (dutasteride) and GSK2285985 (fixed dose combination of dutasteride [GI198745] and tamsulosin [GI138525])" will be referenced; any deviations will be noted within this RAP.

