4. ANALYSIS POPULATIONS

Analysis populations are defined in the following table.

Population	Definition / Criteria	Analyses Evaluated
Intent-To-Treat (ITT)	
 Comprised of all randomized subjects regardless of whether or not treatment was administered This population will be based on the treatment to which the subject was randomized. Any subject who receives a treatment randomization number will be considered to have been randomized. 	
 All.
Per-Protocol (PP)	
 Comprised of all ITT subjects who comply closely with the protocol. Specifically this includes ITT subjects who do not have a deviation which requires exclusion from the PP population. Protocol deviations that would exclude subjects from the PP population are defined in Section 4.1.3 (Deviations which Require Exclusion from the Per-Protocol Population) and Appendix 1 (Exclusions from the Per-Protocol Population). The PP population will not be analyzed if this population comprises more than 80% of the ITT population. 	
 Primary efficacy endpoint only if this population comprises 80% or less of the ITT Population. Details on specific summaries and analyses are outlined in Section 7, Primary Statistical Analyses.

NOTES :

- 'All Enrolled Subjects' is referenced in at least one tabular summary. Enrolled subjects include those who entered placebo run-in phase and/or who were randomized.

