4.1. Protocol Deviations

4.1.1. Inclusion / Exclusion Criteria Deviations

All inclusion / exclusion criteria deviations which are recorded on the inclusion / exclusion screens of the eCRF will be summarized and listed. The tabular summary will be in terms of number and percent of Intent-to-Treat population subjects violating any criterion and violating each criterion. Summaries will be output by each of the two randomized treatment groups and overall.

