6.2. Subject Accountability

Summaries for the following will be produced in terms of total number overall:

- enrolled subjects
- subjects who entered placebo run-in phase
- subjects who entered placebo run-in but withdrew prior to randomization.

Enrolled subjects includes those who entered placebo run-in phase and/or who were randomized.

Summaries for the following will be produced by treatment and in terms of total number overall:

- number of subjects who were randomized to double-blind but missed placebo run-in
- number of subjects who were randomized to double-blind but do not have a double-blind treatment start date
- number of subjects who have a double-blind treatment start date but were not randomized
- number of subjects who were randomized to double-blind and did not take at least one dose of study medication
- number of randomized subjects (ITT population) and defined as subjects with a nonmissing treatment number
- number of subjects in the Per-Protocol population.

Summaries of the ITT population will be produced by country and center and output by randomized treatment and overall.

A listing of randomized subjects (ITT population) will be produced and will include the scheduled randomized treatment and the actual randomized treatment. A flag will be included on the listing to indicate if the scheduled treatment differs from the actual

randomized treatment; as well, any such cases will be included as per-protocol deviations.

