7.1.2. Planned Primary Efficacy Statistical Analyses

Endpoint: The primary efficacy parameter is the change from baseline IPSS at Year 2 (Month 24) using the last observation carried forward approach (LOCF) based on the Intent-to-Treat (ITT) population.

[Table 3](#) provides an overview of the planned IPSS summaries and primary efficacy analyses. A list of planned data displays is in [Appendix 15](#): List of Data Displays.

Baseline and change from baseline are defined in [Appendix 6](#). Last observation carried forward (LOCF) and At Visit approaches are defined in [Appendix 7](#).

Note: IPSS timepoints earlier than Month 24, specifically Month 21 – Month 3, in this order, are classified as secondary endpoints. Summaries and analyses of these timepoints will be conducted in same manner and on same outputs as the primary analyses.

Reference [Table 4](#).

Model Specification and Results Presentation: Change from baseline IPSS at each scheduled post-baseline assessment will be compared in terms of combination treatment versus tamsulosin treatment using t-tests from a general linear model (GLM) with effects for treatment, cluster, and baseline IPSS. Two-sided tests at 0.05 level of significance will be conducted.

The adjusted mean estimates (mean and standard error), the adjusted mean difference, and the 95% confidence interval in terms of the adjusted mean difference will be presented. The adjusted mean difference will be in terms of combination treatment minus tamsulosin treatment. The model results will be presented on same tabular summary as the arithmetic mean, standard deviation, median, minimum and maximum. The results will be presented by treatment for each scheduled post-baseline assessment.

IPSS adjusted mean change from baseline will be plotted by treatment for each post-baseline scheduled visit in terms of each LOCF and At Visit approach.

Multiple Comparisons and Multiplicity: Reference [Appendix 11](#), Multiple Comparisons and Multiplicity.

Model Checking and Diagnostics: Reference [Appendix 12](#), Model Checking and Diagnostics for Statistical Analyses.

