8.2. Safety Analyses

Safety summaries and analyses are reported in terms of the following data classifications: adverse events, clinical laboratory assessments (haematology and clinical chemistry), total serum prostate specific antigen (PSA), qualitative breast examination, digital rectal examination, vital signs, suicidality, and post void residual volume.

All safety analyses will be performed using the ITT population unless otherwise specified in text or data display shells. Applicable safety analysis and reporting definitions and presentations within “Program Safety Analysis Plan (PSAP, 2016) for GI198745 (dutasteride) and GSK2285985 (fixed dose combination of dutasteride [GI198745] and tamsulosin [GI138525])” are utilized within this RAP, with any deviations noted.

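### No visible text says that safety is tabulated by treatment received: Section 4 puts every analysis on ITT by randomized arm, and Appendix 5 gives the opposite default

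*SAP*

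**What the plan says.** SAP Section 11.5.2 (Appendix 5) opens with its scope: "The following reporting process and reporting standards details apply to all RAP defined endpoints". Among its reporting standards is the arm rule: "All data will be reported according to the actual treatment the subject received unless otherwise stated".

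Section 4 defines the ITT population as "Comprised of all randomized subjects regardless of whether or not treatment was administered" and adds: "This population will be based on the treatment to which the subject was randomized". The column naming the analyses for ITT covers all of them. The only other population is Per-Protocol, which is used for the primary endpoint alone, and only if it holds 80% or less of ITT. No safety or as-treated population is defined.

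For the primary endpoint, Section 7.1.2 analyses change in IPSS at Month 24 "using the last observation carried forward approach (LOCF) based on the Intent-to-Treat (ITT) population". For safety, Section 8.2 says: "All safety analyses will be performed using the ITT population unless otherwise specified in text or data display shells".

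The SAP provides for detecting errors in treatment. Section 6.2 lists men whose scheduled and actual treatment differ, flags them, and treats them as per-protocol deviations. It also has an accountability row for the "number of subjects who have a double-blind treatment start date but were not randomized". Deviation 02 in Section 4.1.3 is consumption of the wrong treatment, and Appendix 1 notes that the programmatic check for it is possible only once the study is unblinded.

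**The concern.** For nearly all men the two rules give the same answer. They differ for a man who took the other arm's drug: Section 4 keeps him in his randomized arm, and Appendix 5 moves him to the arm whose drug he took.

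The usual practice is to keep efficacy as randomized and to attribute harms to the drug taken. No visible sentence in the SAP makes that split. If Section 4 governs safety, a sexual or breast event in a man assigned to tamsulosin but dispensed dutasteride is counted against tamsulosin. Section 8.2.4.2 describes the Tier 1 events as ones with predefined hypotheses of a treatment effect, and Section 8.2.2 compares AE categories and common AEs by Fisher's exact test. The rates per 100 person-years of study drug exposure would also place that man's exposure in the wrong arm.

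Timing matters as well. The programmatic check identifies these men only after unblinding, so an arm rule left open would be settled by people who can see which events move.

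**Working it through.** The SAP gives no figure to reproduce. The check is a comparison of texts, followed by a short illustration of size.

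**1. Which rule governs.** The Appendix 5 sentence yields to any statement to the contrary. Section 4 is such a statement, since it ties ITT to randomized treatment.

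- *Primary efficacy.* Section 7.1.2 uses ITT, and Section 4 says ITT is by randomized treatment. The result is as randomized, which is correct.
- *Safety.* Section 8.2 uses ITT, and the same Section 4 definition applies. The result is also as randomized, so a man's events count under a drug he may not have taken.
- *What Appendix 5 still governs.* Almost nothing, because Section 4 assigns ITT to every analysis.

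**2. Whether the wording elsewhere settles it.** Some displays name the randomized arms outright, for example Section 4.1.1: "Summaries will be output by each of the two randomized treatment groups and overall". Sections 7 and 8 mostly say only by treatment or by treatment group. A programmer cannot tell from this where the exception to Appendix 5 is meant to apply.

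**3. Men whom neither rule covers.**

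- A man dosed without being randomized has no randomized arm and is outside ITT. Section 6.2 counts him, but every ITT-based safety table leaves him out.
- A man randomized and never dosed is inside ITT but has no treatment received. The Appendix 5 rule therefore cannot be applied to ITT as it stands.

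**4. Size, on assumed inputs.** Let a share f of each arm take the other arm's drug throughout the study, with true event rates p₁ and p₂ on the two treatments. The rates by randomized arm are

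- p₁(1 − f) + p₂f and p₂(1 − f) + p₁f,
- with difference (p₁ − p₂)(1 − 2f).

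Neither f nor the event rates are in the SAP. Take 10% and 4% as an example:

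| f (assumed) | 1 − 2f | Rates by randomized arm | Difference (true 6.00 points) |
|---|---|---|---|
| 1% | 0.98 | 9.94% vs 4.06% | 5.88 |
| 2% | 0.96 | 9.88% vs 4.12% | 5.76 |
| 3% | 0.94 | 9.82% vs 4.18% | 5.64 |

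The formula assumes equal crossover in both arms for the whole study. Appendix 2 shows medication dispensed again at visits about 13 weeks apart, so one wrong container would give only partial exposure and a smaller shift.

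**The case against.** A reader might infer that the two rules contradict each other flatly, that the primary IPSS test could become as-treated, and that one set of results must be wrong whichever rule is followed. The SAP does not support this. The Appendix 5 sentence carries its own exception, and a named population definition naturally overrides a default listed beside decimal places and p-value rounding. Nor are those the only two outcomes. Efficacy by randomized arm under Section 4, with safety by treatment received under Appendix 5, is a reading the text permits, and neither set would then misassign a man who was randomized and dosed. That part of the objection stands.

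It can also be said that the safety rule may be settled elsewhere. Section 8.2 allows exceptions in the display shells and draws on the Program Safety Analysis Plan, and neither is shown. This rules out asserting that the safety tables will be wrong. It does not supply the missing sentence in the SAP.

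Finally, the flags and the accountability row are controls for detecting errors, not forecasts that they will occur. The count of affected men may be zero, and the Per-Protocol analysis excludes men who took the wrong drug. That is fair as to size, but the Per-Protocol analysis covers only the primary endpoint and gives safety no protection.

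**Conclusion.** The concern holds for safety. On the most natural reading, the primary IPSS analysis is as randomized and needs no change. On that same reading, safety events and exposure follow the randomized arm, and men dosed without randomization are in no safety table. The permitted reading that would correct the arm for safety is nowhere stated, and it would still leave those non-randomized men outside ITT.

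The numerical effect is probably small: a 6.00-point difference falls to between 5.88 and 5.64 points if 1% to 3% of each arm took the other drug throughout. Those shares and the event rates are assumptions. The practical stake is the arm in which individual Tier 1 or serious events are counted, where a single case can matter. The conclusion is limited to the visible text, since the shells and the Program Safety Analysis Plan might say more. The point is worth fixing because it is cheap and because the rule should be set before unblinding.

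**What to change.** Make these changes before unblinding:

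- **Section 4.** Limit ITT, by randomized treatment, to study population, efficacy and health outcomes. Add a safety population of all men who took at least one double-blind dose, analysed by treatment actually received. Men dosed without randomization enter it under the treatment they took.
- **Section 8.2.** Replace ITT with the safety population.
- **Section 6.6.** Use the safety population for the exposure and compliance summaries, so that person-time and events follow the same rule.
- **Section 11.5.2.** Limit the sentence on actual treatment to those displays.
- **Men who took both arms' drug.** Specify one rule in advance. An example is the treatment taken for most of the exposure, with a listing of events by the drug being taken at onset. A rule that moves a man on the strength of a single dose would carry over events that began before the error, which is misattribution in the other direction.
- **Shells.** Check that the safety shells agree with the amended text.

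The cost is SAP wording and a second treatment variable in the analysis datasets. No new data are needed.
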